### Prenatal and postnatal growth as precursors of metabolic syndrome:

Metabolic syndrome is defined as the presence of at least three of the following conditions: abdominal obesity, a high triglyceride level, a low high-density lipoprotein, high blood pressure and high fasting blood sugar. Cardiovascular risk in adults (including signs of metabolic syndrome) is associated with low BW, small size for GA and prematurity and increases with weight gain by 3 years of age. Some authors found no independent association between weight or length at term age and blood pressure in adulthood. In contrast, rapid postnatal weight gain during the first 1.5-3 postnatal months is associated with high systolic blood pressure, obesity, or insulin resistance in adults. Weight gain in excess of linear growth before term corrected age and during the next 3 months is associated with abnormal blood levels of cholesterol, body fat percentage, waist circumference and acute insulin response in young adults. Breastfeeding is associated with better brachial artery endothelial function in adult men. Exclusive breastfeeding for the first 2 months is associated with less frequent non-insulin-dependent diabetes in adult Pima Indians.

In preterm infants, body composition at term age is different than in infants born at term, with a greater proportion of fat mass to lean body weight. In a population study of ELGANs, the amounts of macronutrients (protein, fat and calories) provided in the NICU were independent predictors of growth even after adjusting for severity of illness. Duncan et al have conducted a cross-sectional study including 3 sets of 40 VLBW infants born at Parkland Hospital in 2003-2006 and analyzed at either 1, 2 or 3 years of age. They observed low height and weight z scores for age but increased weight for height, increased ratio of subcutaneous skinfold thickness to abdominal circumference, elevated systolic blood pressure and dysfunctional renal regulation and hyperfiltration, and elevated leptin level, suggesting leptin resistance. Further studies are needed to determine when after birth these occur and whether they predict adult metabolic syndrome.

Microbiome is associated with health and disease in animals and humans. High ratio of Firmicutes to Bacteroidetes (F:B) in stools is associated with obesity and metabolic syndrome in adults. Developmental pattern of the microbiome in infancy is associated with growth rate. Infants who acquire a profile high in Bifidobacterium and Collinsella after 6 months of age have lower adiposity at 18 months of age. Addition of lactobacillus acidophilus to formula increases weight gain in neonates. Several factors affect neonatal microbiome. Mother's own breast milk promotes bacterial diversity in preterm infants compared with formula; pasteurized donor human milk moderately increased bacterial diversity. Antibiotic exposure in neonates reduces stool bacterial diversity and increases risk for obesity. However, no data are available about any effect of individualization of macronutrient intake affects neonatal microbiome.

### Importance of adequate nutrition for growth and neurodevelopment:

In SGA and preterm infants, insufficient weight gain and linear growth and insufficient macronutrient intake in the NICU are associated with growth insufficiency and neurodevelopmental impairment, even after adjustment for other morbidities. However, systematic administration of higher protein intake in the NICU than is recommended may not improve, and very high protein intake (6.0-7.2 gm x kg x day of protein), well beyond the upper maximum of current practice (5.5), may harm neurodevelopment.

### Gap of knowledge:

Limited information is available regarding the impact of higher protein intake on long-term neurodevelopment than is currently recommended. Further studies are needed to evaluate (1) whether or individualizing macronutrient intake to nutrient concentration in human milk is better than adjusting

fortification to serum levels of BUN, and (2) whether protein in enteral feeding should be counted in the total protein intake when only small amount of enteral feed is provided, to improve growth and neurodevelopmental outcome while minimizing the risk for metabolic syndrome in very preterm and SGA infants. No data are available about any effect of individualization of macronutrient intake affects neonatal microbiome.

### **Preliminary Retrospective Data**

Infants <29 weeks GA or < 1000 grams BW, 2008-2012: Parkland Hospital vs. NRN (Table 1):

At birth, infants at Parkland Hospital had similar weight, greater length and fronto-occipital circumference (FOC), and lower ponderal index (PI) [weight in grams x (length in cm) x 100] vs. those in other NRN centers. At 36 weeks PMA, they had greater weight, length and PI, suggesting more weight gain but disproportionate fat deposition.

**Table 1**

	Parkland Hospital		Other NRN Centers	
Gestational age (weeks)	25.3±2.0 (485)**		25.7±1.9 (8704)	
Age of measurement	At Birth	At 36 weeks PMA	At Birth	At 36 weeks PMA
Weight (grams)	843±283 (485)	2323±394 (303)**	834±256 (8699)	2122±409 (5537)
Length (cm)	34.2±2.9 (391)**	43.5±2.3 (261)**	33.4±3.5 (8033)	42.6±3.1 (5135)
FOC (cm)	24.1±1.9 (429)**	30.9±1.5 (283)	23.7±2.2 (7861)	30.9±2.0 (5261)
Ponderal Index	2.08±0.7 (434)*	2.83±0.48 (279)**	2.23±0.69 (8352)	2.74±0.53 (5328)

**Table 1.** Numbers are mean ± SD (n). \* P< 0.01; \*\* P < 0.001 vs. other NRN Centers, Student t-test. Abbreviations: NRN, Neonatal Research Network; PMA, postmenstrual age; FOC, fronto-occipital circumference

Retrospective data from Parkland Hospital NICU 2004-2013 (vs. Olsen & Holston curves):

- Term infants: A PI > 90th percentile was observed in 19% of the neonates, twice the expected proportion. PI was greater in Hispanics and non-Hispanic Whites vs. other groups (**Table 2**).

**Table 2**

Race/ethnicity	Hispanics	Non-Hispanic Whites	African Americans	Asians
Ponderal index	2.68±0.39* (2326)	2.67±0.39* (1710)	2.61±0.40 (791)	2.56±0.33 (128)

Numbers are mean ± SD (n); \*P<0.05 vs. African-Americans and Asians, ANOVA followed by Tukey test

- Preterm infants < 35 weeks GA born 2004-2013 and discharged home (Table 3):

*Weight gain velocity* but not *linear growth* was lower in 29-34 weeks GA with appropriate BW for GA (AGA) infants than in SGA or 23-28 weeks GA infants. *Growth insufficiency* or *small FOC at discharge* was more frequent in SGA vs. AGA infants and in 23-28 weeks GA vs. 29-34 weeks GA infants. *Disproportionate growth* was more frequent in 23-28 weeks GA vs. 29-34 weeks GA infants.

**Table 3**

GA (weeks) and Size for Age	<29 weeks AGA	<29 weeks SGA	29-34 weeks AGA	29-34 weeks SGA	P values
Growth insufficiency at D/C	28% (305)	94% (17)	8% (2784)	69% (304)	***, ***
Small FOC at D/C	5% (325)	53% (17)	2% (2880)	17% (319)	***, ***
Disproportionate growth at D/C	36% (354)	41% (22)	5% (2886)	5% (320)	0.96. ***

Weight gain velocity (gxkg  xd  )	13.3±1.9 (470)	13.5±2.4 (48)	7.4±6.0 (2989)	13.1±3.3 (355)	***,***,***
Linear growth velocity (cm/week)	1.0±0.2 (459)	1.0±0.2 (47)	0.8±1.0 (2949)	0.9±0.6(354)	0.46,0.06,0.24
Change in weight z score#	-0.42±0.67 (326)	+0.52±2.31 (17)	-0.43±0.43 (2893)	+0.14±0.38 (319)	***, **, **
Change in length z score #	-1.03±0.79 (325)	-0.84±0.96 (17)	-0.32±0.76 (2862)	-0.23±0.79 (319)	0.15,***, 0.60
PI at birth	2.21±0.29 (470)	2.14±0.21 (48)	2.36±0.31 (2988)	2.17±0.30 (356)	***, **, *
PI at D/C	2.90±0.35 (459)	3.15±0.80 (47)	2.45±0.29 (2952)	2.52±0.33 (354)	***,***,***
Change in PI (birth to D/C)	0.69±0.41 (459)	1.01±0.76 (47)	0.09±0.40 (2949)	0.35±0.42 (354)	***,***, 0.34

Abbreviations: GA, gestational age; AGA, appropriate for gestational age; SGA, small for gestational age; #, from birth to discharge; D/C, discharge; d, days: FOC, fronto-occipital circumference. Continuous variables are presented as mean±SD (number); comparisons include 2-way ANOVA; P values are shown as: \*\*\*, < 0.001, \*\* < 0.01, \* < 0.05 for SGA vs. AGA; <29 weeks vs. 29-34 weeks; and interaction GA vs. size for age, respectively. Categorical variables are presented as % (total N); comparisons were done using logistic regression; p values are shown as \*\*\*, < 0.001 for comparisons SGA vs. AGA and <29 weeks vs. 29-34 weeks.

In multivariate analyses (n=3809) taking into account GA and BW z score, the presence of a morbidity\* affecting growth (n=464) was significantly (P<0.001) associated with greater increase in PI from birth to discharge and greater odds of growth insufficiency at discharge.

\* chronic lung disease, intestinal obstruction, gastrointestinal surgery, necrotizing enterocolitis, heart surgery, shunt for hydrocephalus

#### □ VLBW infants : BW < 1500 grams born in 2004-2013 and discharged home (**Table 4**):

**Table 4** Many patients had growth insufficiency, small FOC and disproportionate growth at discharge.

GA	Growth insufficiency	Small FOC	Disproportionate growth	Weight gain	Linear growth	PI at birth	PI at D/C	Change in PI
28.8±2.7	26% (999)	7% (1062)	18% (1113)	13.5±3.2	1.0±0.4	2.19±0.30	2.75±0.39	0.56±0.44

### 3. Concise Summary of the Project:

Study design: Randomized trial: Following parental consent, infants will be double blind randomized with 1:1 allocation using a stratified permuted block design by computer, using opaque envelopes. Stratification will be by GA: 23-286/7 and 29-346/7 weeks.

Hypotheses: This study is designed to test the hypothesis that, in preterm infants with gestational age < 29 weeks or with gestational age < 35 weeks and small for gestational age, weight gain velocity from birth to 36 weeks of postmenstrual age will increase by 2 g x kg x day and length gain will increase by 0.2 cm per week with individualized nutrient supplementation. Secondary hypotheses are that individualized nutrition will improve growth and neurodevelopmental outcome and reduce the risk of disproportionate growth and metabolic syndrome.

#### Primary study endpoint (Aim 1):

- Growth velocity (rate of weight gain [g x kg x day] and length velocity [cm x week]) from birth to 36 weeks of PMA or discharge (if discharge is earlier than 36 weeks) will be calculated using Patel's geometric method.

#### Secondary endpoints (Aim 2):

In the NICU:

- Disproportionate growth (abdominal circumference, subscapular skinfold and BMI greater than their respective 90th percentiles for age) at discharge or 36 weeks of PMA (whatever comes first)
- Air displacement plethysmography at discharge: this will be done using the Pea Pod, a noninvasive instrument that is FDA approved for measuring fat in neonates and infants. This apparatus measures body volume; taking into account body weight and accepted assumptions, the analysis generates the percentage of fat and lean body mass. This is the gold standard method for body composition in neonates and young infants, for which normative data are available.
- Blood pressure (systolic and mean, calm or sleeping) at 36 weeks PMA and discharge
- Hypertension, defined as systolic blood pressure >99th percentile for PMA for at least 24 hours while sleeping or calm
- Serum levels of cholesterol, fats, cystatin C, adipokines and some blood markers that may indicate a higher risk for development of diabetes or metabolic syndrome at discharge or 36 weeks of PMA, whatever comes first; these blood samples will be obtained at the same time as other blood samples for clinical indication

At the Follow-up Clinic (Thrive Clinic, [name]), a state-of-the-art facility with >95% follow-up rate, at 6 months, 12 & 36 months chronological age & 18-26 months adjusted age (PNA corrected for prematurity):

- Body composition using Pea Pod at 6 months of age
- Neurodevelopment (Bayley III) scores (cognitive and language composite) at 18-26 months adjusted age
- Findings suggestive of metabolic syndrome: disproportionate growth (excessive fat mass) and high systolic blood pressure at each visit;
- Serum levels of cholesterol, fats, cystatin C, adipokines and some blood markers that may indicate a higher risk for development of diabetes or metabolic syndrome at 1 and 3 years of age (half a teaspoon of blood); these blood samples will be obtained at the same time as other blood samples for clinical indication

Measurement of nutrients in human milk: At present there are no Food and Drug Administration (FDA) approved devices for the analysis of nutrient content in human milk samples obtained in the NICU. The SprectraStarTM Neonatal Analyzer has been validated and has been used in a RCT. Twice a year, the device will be calibrated against control human milk samples purchased from the Ohio Milk Bank and analyzed using state-of-the art chemical analysis, and variability will be assessed. The UT Southwestern Institutional Review Board (IRB) has classified this device as non-significant risk device.

#### Other measurements:

- Maternal pre-pregnancy weight, height, body mass index (BMI), weight gain during pregnancy, placenta weight, antenatal and perinatal maternal diseases (e.g., diabetes mellitus, preeclampsia), antenatal steroids, intrauterine growth restriction
- GA: best obstetrical estimate (if no prenatal care, new Ballard score)
- Race/ethnicity, insurance, socioeconomic status, maternal education
- Birth & 36 weeks measurements: weight, FOC, length (obtained on stadiometer within 3 days of birth; up to 7 days of life in patients who are initially critical and unstable), BMI (using BW and length on stadiometer to improve accuracy), abdominal circumference, mid-arm circumference

- Comparison of relative changes [(36-week measurement – birth measurement)/birth measurement] in weight, length and FOC from birth to 36 weeks PMA; change in z score in weight, length and FOC
- Serial measurements of weight, length (using stadiometer for calculating BMI), linear growth estimated from the percent change of heel-knee height measurements in the critically ill unstable neonate, FOC, arm and thigh muscle circumference, abdominal circumference
- At discharge: triceps and subscapular skinfold thickness
- Nutritional tests: weekly BUN adjusted if necessary for renal dysfunction (see study intervention), albumin, electrolytes, phosphate, alkaline phosphatase; if the latter two tests suggest osteopenia: bone radiogram; vitamin D levels will be considered in severe cases.
- Days without feeding, human milk vs. formula, days to full feeds, days of central line & parenteral nutrition, refeeding syndrome, metabolic acidosis, osteopenia of prematurity, micronutrient deficiency (e.g. zinc, essential fatty acids, carnitine), mineral deficiency (e.g., magnesium), type and composition of feeding at discharge
- Morbidities affecting growth or neurodevelopment, e.g., congenital infection, genetic anomaly, organ failure, bronchopulmonary dysplasia, antibiotics/sepsis, major surgery, intestinal perforation, necrotizing enterocolitis, severe intraventricular hemorrhage, periventricular leukomalacia, congenital anomalies, systemic steroids
- Cumulative percentage of enteral intake as breast milk in the NICU, which may influence the effect of the intervention and glucose, lipid and apolipoprotein metabolism.
- Stools will be collected and frozen for later analysis of microbiome diversity, Firmicutes:Bacteroidetes ratio and metagenomics. Samples will be collected every other week from randomization to discharge.
- Follow-up at 12 and 36 months chronological age and at 18-26 months adjusted age:
- Weight, length, FOC, abdominal circumference, skinfold thickness, two calm blood pressure measurements using Doppler amplification with the exact same protocol as previously described, history of steroids and antibiotics at each visit
- Neurodevelopment (Bayley III) cognitive and language composite scores at 18-26 months
- Serum levels of cystatin C, creatinine, cholesterol (total, LDL, HDL), triglycerides, Leptin, Adiponectin, Resistin, IL-6 and TNF alpha at 1 and at 3 years of age (half a teaspoon of blood)
- Whole-body Dexascan to analyze body composition including percentage of fat at 1 and 3 years of age

Procedures: Patients will be randomized to either (a) Optimized and individualized nutrition by adjusting milk fortification based on daily measurements of macronutrients in mother's own milk or information on milk from the milk bank or (b) optimized (standard of care at Parkland), i.e., assuming macronutrient concentration in human milk based on available literature and summing enteral and intravenous protein intake. Patients will be followed for growth parameters in the neonatal intensive care unit and for growth, neurodevelopment and signs suggestive of metabolic syndrome in the low birth weight clinic until 3 years of age.

Maximum number of consented patients: 200; this will allow attrition for comfort care, deaths before 36 weeks PMA and withdrawal from the study; we expect to recruit approximately 150 patients into the study with a goal of 100 patients reaching endpoint at 36 weeks PMA

Duration of the study: 6 years: recruitment for 2 years, follow-up for 3 years, analysis for 1 year

Reason for removing from the study: comfort care, withdrawal by the parents

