#### Secondary endpoints (Aim 2):

In the NICU:

- Disproportionate growth (abdominal circumference, subscapular skinfold and BMI greater than their respective 90th percentiles for age) at 36 weeks of PMA or discharge if patient is discharged earlier than 36 weeks PMA
- Body composition analysis using air displacement plethysmography (Pea Pod)
- Blood pressure (systolic and mean, calm or sleeping) at 36 weeks PMA and discharge
- Hypertension, defined as systolic blood pressure >99th percentile for PMA for at least 24 hours while sleeping or calm
- Blood sample for measurements of cholesterol, fats, cystatin C, adipokines and some blood markers that may indicate a higher risk for development of diabetes or metabolic syndrome at discharge or 36 weeks of PMA, whatever comes first;
- Bacterial diversity and ratio of Firmicutes to Bacteroidetes (F:B) in stool samples (1) at 28 days of age and (2) at 36 weeks or discharge if earlier than 36 weeks
- Body composition analysis using air displacement plethysmography (Pea Pod) at 36 weeks of PMA or discharge if patient is discharged earlier than 36 weeks PMA

At the Follow-up Clinic (Thrive Clinic, [name]), a state-of-the-art facility with >95% follow-up rate, at 6, 12, & 36 months chronological age & 18-26 months adjusted age (PNA corrected for prematurity):

- Neurodevelopment (Bayley III) scores (cognitive and language composite) at 18-26 months adjusted age
- Findings suggestive of metabolic syndrome: disproportionate growth (excessive fat mass) and high systolic blood pressure at each visit at 6 months, 1, 2 and 3 years of age
- Serum levels of cholesterol, fats, cystatin C, adipokines and some blood markers that may indicate a higher risk for development of diabetes or metabolic syndrome at 1 and 3 years of age
- Body composition analysis using air displacement plethysmography (Pea Pod) at 6 months of age
- Body composition analysis using Dexascan (Hologic Horizon A) at 1 and 3 years of age □ Relationship between stool bacterial diversity and F:B ratio, growth and obesity Stopping Rules:

- Less than 10 patients recruited in 12 months
- Mortality in enrolled patients significantly higher than in non-enrolled patients ( $P<0.01$ )
- More frequent necrotizing enterocolitis in enrolled patients ( $P<0.01$ )

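### Disproportionate growth is assessed at 36 weeks PMA or earlier discharge, but the written NICU schedule places its skinfold component at discharge

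*Combined protocol and SAP*

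**What the plan says.** **Endpoint definition.** The secondary endpoints under Aim 2 appear twice, in Section 1 (Introduction and Purpose) and Section 3 (Concise Summary of the Project). Section 3 names the components: "Disproportionate growth (abdominal circumference, subscapular skinfold and BMI", each to exceed its 90th percentile. On timing, Section 1 has "percentiles for age) at 36 weeks of PMA or discharge if patient is discharged earlier than 36 weeks PMA", and Section 3 has "percentiles for age) at discharge or 36 weeks of PMA (whatever comes first". The two agree: 36 weeks PMA, or discharge for infants who leave sooner.

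**Measurement schedule.** Under Other measurements in Section 3, one entry covers birth and 36 weeks. It opens "Birth & 36 weeks measurements: weight, FOC, length" and ends with "BMI (using BW and length on stadiometer to improve accuracy), abdominal circumference, mid-arm circumference". A further entry lists serial measurements, including abdominal circumference. Neither contains a skinfold. The only NICU entry for skinfolds is "At discharge: triceps and subscapular skinfold thickness". Skinfolds come up again only at the follow-up clinic visits.

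**Pea Pod.** This is a separate body-composition endpoint. Section 1 lists it twice for the NICU, once with no time and once as "plethysmography (Pea Pod) at 36 weeks of PMA or discharge if patient is discharged earlier than 36 weeks PMA". Section 3 has "Air displacement plethysmography at discharge: this will be done using the Pea Pod".

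**The concern.** The endpoint definition and the measurement list disagree about when one of three required components is taken. For an infant who stays beyond 36 weeks PMA, two components are scheduled at the endpoint time and the third at a later, variable date.

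Staff who follow the measurement list leave the analyst two choices. One is to treat the skinfold as missing at 36 weeks. The other is to bring in the discharge value and build a composite from two ages. The second is not neutral by design, because the gap between the measurements depends on length of stay, which is determined after randomisation.

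This endpoint is one of those that address the Aim 2 question of whether individualised nutrition reduces excess fat in the NICU. A 36-week skinfold that was not taken cannot be recovered at analysis.

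**Working it through.** The plan states no figure on this point, so the check sets the texts side by side.

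**Step 1. Are 36 weeks and discharge different occasions in this plan?** Yes. Both endpoint lists take blood pressure at 36 weeks PMA and also at discharge. Where the plan means the earlier of the two, it says so, as it does for the in-hospital blood markers. The measurement list also gives 36 weeks and discharge separate entries. An entry for discharge alone therefore cannot safely be read as shorthand for the 36-week session.

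**Step 2. Which components are scheduled at the endpoint time?**

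- Infant discharged before 36 weeks: discharge is the endpoint time, so there is no conflict over the skinfold.
- Infant in hospital beyond 36 weeks: BMI is scheduled at 36 weeks; abdominal circumference is scheduled at 36 weeks and serially; subscapular skinfold is not scheduled until discharge.

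**Step 3. Which infants become unclassifiable?** The components are joined by *and*. For an infant with no 36-week skinfold:

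- BMI or abdominal circumference at or below the 90th percentile: negative, whatever the skinfold.
- BMI and abdominal circumference both above the 90th percentile: undetermined.

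The gap therefore falls on every potential event among infants still in hospital, and on no one else. If the classifiable infants were kept and the undetermined ones dropped, or if a missing skinfold were counted as not exceeding the cut-off, this group would contribute no events at all.

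**Step 4. How many infants?** The documents do not give the share still in hospital at 36 weeks PMA, or the share above the 90th percentile on both other components. Table 3 gives historical counts for infants who went home, from which the share born before 29 weeks among the three eligible groups can be computed:

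- weight-velocity row: (470 + 48)/(470 + 48 + 355) = 518/873 = 59%
- disproportionate-growth row: (354 + 22)/(354 + 22 + 320) = 376/696 = 54%
- growth-insufficiency row: (305 + 17)/(305 + 17 + 304) = 322/626 = 51%

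This range of 51% to 59% describes the gestational-age mix only. It is not an estimate of how many infants would be unclassifiable.

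**Step 5. Pea Pod.** For an infant in hospital beyond 36 weeks, Section 1 puts the measurement at 36 weeks and Section 3 puts it at discharge. Pea Pod is not a component of disproportionate growth, so this conflict has no bearing on Step 3.

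**The case against.** The strongest reply is that the endpoint lists are the governing text. Both place the skinfold at 36 weeks or earlier discharge, and a team working from them would measure it then. The measurement list does not say that skinfolds are taken at discharge and at no other time. Section 4 (Study intervention) ties NICU data collection to a separate quality-improvement protocol, and Section 10 refers to an attached data collection form. Neither was available for this review, and either may include a 36-week skinfold. This stands as a limit: the finding concerns the written schedule, not what staff will do. It does not remove the need to correct the measurement list.

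A second reply is that the percentiles are specific to age, so a discharge skinfold could be judged against its own age reference. This stands in part. It deals with age for that single component, but the composite would still describe the infant on two dates rather than at 36 weeks.

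A reader might infer that the endpoint cannot be computed for half or more of the infants. The documents do not support that. Infants at or below the 90th percentile on BMI or abdominal circumference can still be classed negative, and no inpatient share is given.

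A reader might also infer a bias between arms, on the ground that faster growth brings earlier discharge. Nothing in the documents establishes that link. Unequal timing between arms is possible but not shown.

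**Conclusion.** The inconsistency is real and worth correcting. On the written schedule, infants still in hospital at 36 weeks PMA have no skinfold at the endpoint time, and those above the 90th percentile on both other components cannot be classified as the endpoint is defined. This rests on two assumptions: that the three components must all be exceeded, and that the documents not supplied do not add a 36-week skinfold. If the three measures were instead reported separately, only the skinfold would be affected.

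The number of infants affected cannot be derived from the documents. The Pea Pod mismatch is a second, separate timing conflict and should not be read as blocking the disproportionate-growth endpoint. The age question bears more directly on Pea Pod, because its endpoint entries do not call for an age-specific percentile.

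These are secondary endpoints, and the documents do not rank them. The primary growth-velocity endpoint does not use skinfolds or Pea Pod and is unaffected.

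**What to change.** Reconcile the secondary endpoint lists in Sections 1 and 3 with Other measurements in Section 3:

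- Add the subscapular skinfold to the 36-week measurements, taken at discharge for infants who leave earlier, in the same session as BMI and abdominal circumference.
- State one time for Pea Pod and use it in both endpoint lists.
- Check that the quality-improvement protocol and the data collection form carry the same times.

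The cost is schedule wording. The skinfold is already planned and would move to an existing session. If discharge values are also wanted, the downside is one more brief caliper reading for infants who stay beyond 36 weeks.

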### *Study intervention:*

Patients will be randomized to either

- (1) Optimized and individualized nutrition by adjusting milk fortification based on daily measurements of macronutrients in mother's own milk or information on milk from the milk bank
- (2) Or optimized (standard of care at Parkland), i.e., assuming macronutrient concentration in human milk based on available literature and summing enteral and intravenous protein intake

*Data collection in the NICU will be identical to that for other patients who are part of the QI protocol submitted to the IRB: STU 102014-045: Optimizing Individual Nutrition in Preterm Very Low Birth Weight Infants.*

*Procedures done for research* during follow up until 3 years of age include:

- skinfold thickness measurements
- Neurodevelopment exam (Bayley III cognitive and language composite scores) for patients who are not enrolled in the NICHD follow-up study (<27 weeks GA)
- (only if parent checks the box on the consent form): half a teaspoon of blood sample; this blood will be kept in the freezer at -80 degrees for 10 years for measurement of cholesterol, fats, and

some blood markers that may indicate a higher risk for development of diabetes or metabolic syndrome.

- (only if parent checks the box on the consent form): whole-body Dexascan to analyze body composition including percentage of fat at 1 and 3 years of age. The radiation dose is approximately 1% of the Annual US Avg. Natural Background.

Due to COVID-19 restrictions, the 18-26 months Adjusted Age Follow-up extended up to one year from the end of the study window.

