The PI will send the data safety reports to the IRB.

Reporting Unanticipated Problems, Adverse Events, Protocol Deviations and Protocol Violations:

- PI will report adverse events to the IRB immediately
- PI will report safety reports and DSMC reports to the IRB.

Stopping Rules:

1. Specific stopping rules:

- Less than 10 patients recruited in 12 months
- Mortality in enrolled patients significantly higher than in non-enrolled patients ( $P<0.01$ )
- Necrotizing enterocolitis in enrolled patients more frequent than in non-enrolled patients ( $p<0.01$ )

1. Action indicated by the specific stopping rule:

PI will notify the IRB, all research team members and the funding agency.

Procedures and Time Frames for Communicating Outcomes:

An open report of the accrual and demographics will be provided to the DSMC by the research team. A closed report of mortality and necrotizing enterocolitis will be provided to the DSMC by a statistician.

The report of the DSMC will be provided to the PI and to the IRB.

Precautions for Maintaining Data Integrity:

Random selection of data will be checked by the PI and the DSMC for completeness and integrity.

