#### **14. Biostatistics:**

The primary outcome variable (growth) will be analyzed by intention to treat (i.e., as randomized). Continuous variables including the primary outcome will be analyzed using Student's t-test or analysis of variance and a generalized linear model (to determine the effect of the intervention while taking into account co-variates and confounding variables). Dichotomous variables will be analyzed using chi-square analysis and by estimating relative risk using robust Poisson regression in a generalized estimating equation model. Subgroup analyses will be done to compare the 3 strata (AGA 23-28 weeks, SGA 23-28 weeks and SGA 29-34 weeks) and to compare SGAs due to insufficient calories (e.g., preeclampsia, low placental insertion) vs. constitutionally small neonates (e.g., congenital infection, genetic anomaly, short parents). A probability value  $<0.05$  will be considered statistically significant. Secondary outcome variables will be analyzed according to appropriate statistical techniques.

Sample size analysis: Based on the number of patients delivered at Parkland during the last 10 years, we expect that 342 (1140x3/10) eligible neonates will be delivered over 3 years. We anticipate enrolling half in the study and expect that 2/3 will survive to 36 weeks PMA. Thus we will enroll 150 patients to yield a 100 patients available for the primary outcome and to have 80% power using 2-tailed Student t-test (alpha error 0.025) to detect an increase in weight gain velocity in the NICU by  $2 \text{ g} \times \text{kg}^{-1} \times \text{day}^{-1}$  (standard deviation  $3 \text{ g} \times \text{kg}^{-1} \times \text{day}^{-1}$ ) and 95% power (alpha error 0.001) to detect an increase in length velocity by 0.2 cm per week (standard deviation 0.2 cm per week), taking into account clustering due to twins and multiples. We will have  $>80\%$  power for both outcomes (alpha error 0.05).

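### The 2-year recruitment period in Section 3 does not match the 3 years of births that Section 14 uses for the same target of 150 enrolled

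*Combined protocol and SAP*

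**What the plan says.** The end of Section 3 (Concise Summary of the Project) sets the calendar: "Duration of the study: 6 years: recruitment for 2 years, follow-up for 3 years, analysis for 1 year". The three parts add up to the total (2 + 3 + 1 = 6), so the 2 years is not an isolated slip. Just above that line, the same section gives the target: "we expect to recruit approximately 150 patients into the study with a goal of 100 patients reaching endpoint at 36 weeks PMA". It also sets a ceiling: "Maximum number of consented patients: 200".

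The sample size paragraph of Section 14 (Biostatistics) reaches the same target by a different route. It scales 1140 eligible births in 10 years to 342, which it describes as "eligible neonates will be delivered over 3 years". It continues: "We anticipate enrolling half in the study and expect that 2/3 will survive to 36 weeks PMA". It concludes: "Thus we will enroll 150 patients to yield a 100 patients available for the primary outcome".

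The only recruitment-related rule for stopping, in Sections 1 and 10, is "Less than 10 patients recruited in 12 months".

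**The concern.** Both sections give 150 enrolled and 100 evaluable, but one allows 2 years to get there and the other counts 3 years of births. The factor of 3 is written into the Section 14 calculation, so neither figure looks like a misprint, and no other part of the document reconciles them. At the plan's own rates, the period in Section 3 does not deliver the number in Section 3.

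What is at stake is mainly the timeline and the resources tied to it. The document also does not say whether the enrolment target or the calendar ends recruitment. That matters only if the calendar were to win, because the yield would then fall below the number on which the power statement rests.

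**Working it through.** **Inputs.** From Section 14: 1140 eligible births in 10 years; half enrolled; two thirds surviving to 36 weeks; target 150 enrolled and 100 evaluable; weight gain difference 2 g/kg/day with SD 3, two-sided alpha 0.025, stated power 80%. From Section 3: 2 years of recruitment and 6 years in total. Allocation is 1:1.

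**Reproducing the plan's figures.**
- Eligible over 3 years: 1140 × 3/10 = 342, as stated.
- Evaluable from 150 enrolled: 150 × 2/3 = 100, as stated.
- Enrolled over 3 years at one half: 342/2 = 171; evaluable 171 × 2/3 = 114. Three years therefore covers the target, with 21 enrolled and 14 evaluable to spare.

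**Annual rates.** Eligible 1140/10 = 114; enrolled 114/2 = 57; evaluable 57 × 2/3 = 38.

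**Yield by recruitment period.**

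| Recruitment | Eligible | Enrolled | Evaluable |
|---|---|---|---|
| 2 years (Section 3) | 228 | 114 | 76 |
| 3 years (Section 14) | 342 | 171 | 114 |
| Target | – | 150 | 100 |

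Two years falls short by 150 − 114 = 36 enrolled and 100 − 76 = 24 evaluable, 24% in each case.

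**Time to target.** 150/57 = 2.63 years. With the other two phases unchanged, the total is 2.63 + 3 + 1 = 6.63 years; with the full 3 years of recruitment it is 3 + 3 + 1 = 7 years.

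**Enrolment fraction needed to keep 2 years.** 150/228 = 66%, against the anticipated half.

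**Power, only if recruitment closed at 2 years.** Two-sided t-test for weight gain velocity, noncentral t distribution, no clustering, noncentrality (2/3) × √(n/2) with n per arm:
- 100 evaluable, n = 50: noncentrality 3.33, power 85% at alpha 0.025.
- 76 evaluable, n = 38: noncentrality 2.91, power 73% at alpha 0.025.

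The like-for-like comparison is 73% with 85%. The stated 80% is said to allow for twins and multiples, but the document gives no design effect, so none is applied here. At alpha 0.05 and 76 evaluable, power without clustering is 82% for weight and 99% for length, so the closing statement of Section 14 that both exceed 80% would still hold on that basis.

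**The case against.** The strongest reply is that nothing scientific depends on the duration line. Section 14 commits to enrolling 150, so recruitment to target is the natural reading. Endpoint, randomisation, analysis and patient numbers are then untouched, and only a planning period is about 0.6 years short. This stands, and it is why the point is minor.

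A second reply is that 76 evaluable rests on a round survival figure. Table 3 lists 470 + 48 + 355 = 873 infants in the three eligible groups with a weight gain velocity, among those discharged home in 2004–2013. If the 1140 births cover the same decade, which the document does not say, 873/1140 = 77% reached discharge. Two years would then yield about 87 evaluable, with 79% power for weight at alpha 0.025 without clustering. Table 1 points the other way for a less mature group: 303 of 485 Parkland infants (62%) have a weight at 36 weeks. So 76 is what the plan's assumption implies, not a firm forecast. Neither table changes the time needed to enrol 150.

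Third, the planning words are approximate, and up to 200 may be consented. But 114 is 24% below 150, and a ceiling on consents adds no births and does not raise the enrolment fraction.

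**Conclusion.** The inconsistency is real and the correction is minor. At the rates in Section 14, 150 enrolled takes about 2.6 years, not 2, and the 6-year total is short by the same 0.6 years. This rests on 114 eligible births a year and half of them enrolling.

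Two stronger readings are tempting and are not supported:

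- A reader might infer that the trial is underpowered or its sample size wrong. The 150 and 100 agree across sections, and power is unchanged if recruitment runs to target. The drop to about 73% for weight needs a close at 2 years and the two-thirds survival figure. Beyond the planned duration itself, nothing in the document orders such a close; the accrual stopping rule concerns fewer than 10 patients in 12 months, far below the expected 57.
- A reader might infer that the follow-up part of the duration line is also wrong, because under COVID-19 restrictions "the 18-26 months Adjusted Age Follow-up extended up to one year from the end of the study window". That is an allowance for one visit. The planned schedule still ends at 36 months, in line with 3 years of follow-up. A longer total would need one particular reading of the allowance and the last infant enrolled using all of it. Nor does the allowance extend recruitment, so it does not resolve the mismatch.

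**What to change.** Make the duration line in Section 3 agree with Section 14, in one of two ways:

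1. State that recruitment continues until 150 infants are enrolled, expected to take about 2.6 years and to fall within the 3 years that Section 14 uses, and lengthen the 6-year total to match.
2. Keep 2 years, and restate the expected yield (114 enrolled, 76 evaluable) and the power that goes with it.

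The first is the simpler, because it leaves the sample size and power statement as they are. It also makes clear that the target, not the calendar, ends recruitment. Either is a small wording change that adds no patients to the plan. The cost is a stated timeline up to about one year longer, with the staffing that implies, or else a less favourable stated power.
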